Correlating IASIS-related changes in MEG slow-wave source imaging and PCS in mTBI: Correlation analyses will be performed to examine the neuronal correlates of changes in MEG slow-wave generation and PCS scores in Veterans with mTBI in both IASIS and Sham groups. Specifically, we will correlate the changes in the total abnormal MEG Z-scores as well as voxel-wise Z-score MEG source imaging measures with changes in PCS due to IASIS treatment, by comparing PCS scores from post-treatment follow-up (Visit 15) with the baseline (Visit 2) exams. We predict that reduction in MEG slow-wave generation will correlate with reduced total PCS score as well as specific symptom scores (e.g., sleep disturbance, post-traumatic headache, photophobia, and memory problem symptoms) (Hypothesis 6). The voxel-wise analysis may provide important spatial information of the slow-wave generation related to each PCS category. Linear regression analyses will be performed for the correlation analysis, and FDR will be used to control family-wise error [85] using correct $q < .05$. We predict that in mTBI-IASIS group, but on

in the sham group, reduction in MEG slow-wave generation will correlate with reduced symptoms. Preliminary data presented in Section C.6.2 and Fig. 6C support this hypothesis.

Correlating IASIS-related changes in MEG slow-wave source imaging and cognitive functions in mTBI: We will study the relationship between changes in MEG slow-wave generation with those in neuropsychological exam scores between post-IASIS (Visit 15) and baseline exams (Visit 2). For neuropsychological tests that differentiate HC and mTBI groups, we will perform linear regression analysis, where treatment-related changes

in neuropsychological test scores are used to predict the changes in MEG measures including voxel-wise slowwave Z-score (FDR corrected for family-wise error) and the total abnormal MEG Z-scores. We also predict that in mTBI-IASIS group, but not in the sham group, reduction in MEG slow-wave generation will correlate with improvement in the different cognitive domains that govern functioning.

D.7 Examining the effects of Covariate Variables on IASIS treatment and Exploratory Analyses in mTBI

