Covariate variables to be included in above statistical analysis: Age, gender, education, combat exposure (DRRI-2), socioeconomics, OSU TBI-ID for lifetime history of TBI, ASSIST and AUDIT for alcohol and substance uses, and order of mTBI to PTSD will be added as covariates in the linear regression and ANOVA analyses in Sections D.4 - D.6. However, since these variables will be matched during our group assignment, we do not predict they will have major impact to the results of statistical analyses.

Exploratory studies: We will add 10 minutes rs-fMRI in Visit 2 to our existing MRI acquisition on a 3T system in the two mTBI groups, and use the data for exploratory FC analyses of the relationship between rsfMRI and rs-MEG using the approach described in [14]. We will also add an N-back MEG task in Visits 2 and 15 for exploratory analyses of changes in working memory function due to IASIS treatment. We have previously found that changes in rs-MEG neural patterns are highly associated with the working memory performance of the N-back MEG task [110].

D.8 Description and Justifications of Sampling Plan, Power Analysis, and Time Table

For assessing the specificity (1- false-positive rate) of the MEG slow-wave measures on a single-subject basis, the number of HC subjects in the normative database has to be sufficiently large. N=75 will allow us to reliably assess the normative datasets from HC participants. By choosing K=3 in the K-fold cross-validation approach, 2/3 (N=50) will be used to construct the normative database and the remaining 1/3 (N=25) to test the specificity, with reliable performance.

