Power analysis: We don't expect that one set of sample sizes will meet the needs of all 3 aims and 6 hypotheses equally well. Hence, for a proposed set of sample sizes, some hypotheses may be overpowered whereas the others may be adequately powered. We used G*Power (University of Dusseldorf) for the power analysis. The power analyses below show that the N=50 in each of the two mTBI groups (i.e., mTBI-IASIS and mTBI-Sham) provides a good balance for all the hypotheses. For Hypothesis 1, our voxel-wise MEG slowwave source imaging is expected to show substantially higher sensitivity in detecting in mTBI groups than conventional MRI. Based on our preliminary data using McNemar's test in C.2, we expect a large effective size (odds ratio > 50). At two-tailed, $\alpha=0.01$, N=50 in each of the mTBI groups, the estimated power is > 0.98. We also predict high test-retest reliability of MEG slow-wave source imaging measures in N=100 Veterans (50 in each group) that will have two consecutive MEG exams (Visits 2 and 3). Based on our preliminary data in C.4, high level of test-retest reliability (i.e., ICCs ≥ 0.75) is expected in our rs-MEG slow-wave source imaging. In Hypothesis 2, we predict that IASIS treatment will enhance neural healing by initially potentiating slow-wave generation immediately after each treatment session. In Hypothesis 3, we expect that in Veterans in mTBI-IASIS group, but not in mTBI-Sham group, MEG source imaging (voxel-wise and total Z-score) will ultimately show a significant decrease in abnormal slow-waves between pre- and post-treatment exams. Based on preliminary data in C.5 and C.6 (Figs. 6B and 7), for Hypotheses 2 and 3, we expect large effect size (Cohen's $f>0.45$). At two-tailed, $\alpha=0.01$, N=50 in each of the mTBI groups, the estimated power is > 0.98. In Hypotheses 4 and 5, we predict that, compared with the sham group, mTBI participants in the IASIS treatment group will show significantly larger decreases in PCS and PTSD symptoms between baseline and post-treatment assessments. Based on pilot data in C.6 and information from [68], we expect medium-to-large effective size for total the RPQ (Cohen's $f>0.38$) and medium-to-large effective size for PCL (Cohen's $f>0.32$). At two-tailed, $\alpha=0.01$, N=50 in each of the mTBI groups, the estimated power is > 0.95 for total RPQ score, and power > 0.85 for PCL. We will also have power > 0.88 for 5 individual PCS scores (e.g., PSQI for sleep problems, MGPQ for pain, etc.) with the conservative Bonferroni correction. For Hypothesis 6, we expect changes in MEG slowwaves will correlate with PCS scores and cognitive deficits in specific domains in mTBI groups due to IASIS. Based on our preliminary data in C.6 and C.7, we expect medium-to-large effect sizes ($|r| \sim 0.4-0.8$). With N=50 in each mTBI group, two-tailed, $\alpha=0.05$, the estimated powers are > 0.85 for changes in MEG slow-wave correlating with total PCS score or one NP variable. The same level of power can be achieved for 5 symptom individual PCS / NP variables at $\alpha=0.05$, in the conservative case of Bonferroni correction, and for more than 5

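### The stated Hypothesis 6 power of over 0.85 is not reached at an adjusted correlation of 0.4 once the nine or ten planned covariates enter a 50-person arm; it is about 0.75 there and reaches 0.85 only from about 0.45

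*Combined protocol and SAP*

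**What the plan says.** All references are to Section 9 of the combined protocol and SAP.

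- **D.8, power.** For changes in MEG slow-waves against symptoms or cognition, the expected correlation is given as a range, about 0.4 to 0.8. Sample size is 50 in each mTBI arm at two-sided alpha 0.05, and "the estimated powers are > 0.85 for changes in MEG slow-wave correlating with total PCS score or one NP variable". On method it says only "We used G*Power (University of Dusseldorf) for the power analysis". The G*Power procedure, the number of predictors and whether the correlation is adjusted are not given, and the Hypothesis 6 sentences mention no covariates.
- **D.6, analysis.** "Linear regression analyses will be performed for the correlation analysis". The association is predicted in the IASIS arm and not in the sham arm, which agrees with the per-arm sample size in D.8.
- **D.7, covariates.** Age, gender, education, combat exposure, socioeconomics, lifetime TBI history, ASSIST, AUDIT and the order of mTBI to PTSD "will be added as covariates in the linear regression and ANOVA analyses in Sections D.4 - D.6". That is nine variables. Because they are matched at group assignment, "we do not predict they will have major impact to the results of statistical analyses".
- **D.1.2.** The BDI-II score is also to be a covariate in the data analyses, which makes ten.

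**The concern.** The power statement and the planned model do not visibly describe the same test. Nine or ten covariates in a regression on 50 people use degrees of freedom. Because predictor and covariates are all measured quantities, the covariates also absorb part of the predictor's variance by chance overlap within the sample. The second effect is the larger one, and a formula that treats the design as fixed leaves it out.

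Hypothesis 6 is read by setting a positive IASIS arm beside a null sham arm. If the chance of missing a true correlation of 0.4 is about 25% rather than the 15% or less that D.8 implies, a null result in either arm carries less information than the plan suggests. This is also the single-variable test, the most favourable case that D.8 presents for Hypothesis 6.

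**Working it through.** **Inputs.** N = 50 per arm, two-sided alpha 0.05, r = 0.4 as the low end of the stated range, stated power above 0.85 (all D.8). The number of covariates k is 9 (D.7) or 10 (adding BDI-II, D.1.2), at one term each. Complete data on all 50 are assumed.

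**Step 1: reproduce the stated figure.** In the fixed-model regression test, f² = r²/(1 − r²) = 0.16/0.84 = 0.1905, and the noncentrality is N × f² = 50 × 0.1905 = 9.52. With 1 and 48 degrees of freedom, power is 0.856, so the figure reproduces. The exact test for a simple correlation between two measured variables gives 0.835, and the Fisher z approximation 0.828.

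**Step 2: add covariates to the same formula.** The noncentrality stays at 9.52 and only the error degrees of freedom change, to 50 − 2 − k = 39 or 38. Power is 0.853 with either nine or ten covariates. A fixed-model run therefore exceeds 0.85 whether or not the covariates were entered.

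**Step 3: treat predictor and covariates as measured.** A partial correlation with k measured covariates behaves like a simple correlation at sample size n = N − k, here 41 or 40. Power is the noncentral t power with n − 2 degrees of freedom and noncentrality √U × r/√(1 − r²), averaged over U distributed as chi-square with n − 1 degrees of freedom. The mean squared noncentrality for k = 9 is 40 × 0.1905 = 7.62, against 9.52 in step 2.

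| Adjusted r | No covariates | k = 9 | k = 10 |
|---|---|---|---|
| 0.40 | 0.835 | 0.753 | 0.742 |
| 0.43 | 0.890 | 0.819 | 0.809 |
| 0.45 | 0.919 | 0.857 | 0.848 |
| 0.50 | 0.967 | 0.929 | 0.923 |

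Power of 0.85 is reached at an adjusted r of 0.447 (k = 9) or 0.452 (k = 10). At r = 0.4 it would need 62 or 63 people per arm.

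**Step 4: two checks at r = 0.4.**
- Fisher z: arctanh(0.4) = 0.4236. For k = 9, 0.4236 × √(50 − 3 − 9) = 0.4236 × 6.164 = 2.611; subtracting 1.960 leaves 0.651, and power is 0.743. For k = 10 it is 0.731.
- Simulated regressions, 20,000 runs, covariates unrelated to either change score: 0.837 with none, 0.751 with nine, 0.745 with ten.

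**Step 5: let 0.4 be the unadjusted correlation.** Suppose the covariates explain a share R² of outcome variance, independently of the predictor. The squared adjusted correlation is then 0.16/(1 − R²). Simulated power, 10,000 runs per cell:

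| Covariate R² | Adjusted r | k = 9 | k = 10 |
|---|---|---|---|
| 0.05 | 0.410 | 0.774 | 0.769 |
| 0.10 | 0.422 | 0.808 | 0.789 |
| 0.20 | 0.447 | 0.852 | 0.843 |

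The covariates must explain about 20% of outcome variance for power to return to 0.85. The documents give no value for this share, so the rows are a range of assumptions.

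**The case against.** The strongest reply is that the printed number is correct for a recognised formula. Step 2 shows that a G*Power fixed-model run including all the covariates still gives 0.853, whereas the exact simple-correlation test gives 0.835, which is below the claim. A reader might infer from D.8 that a simple correlation was powered and the covariates forgotten. The documents do not support that inference, because neither the procedure nor the number of predictors is stated. What remains is that the fixed-model convention does not suit a regression of one measured change score on another with measured covariates, and it gives too high a power whichever inputs were used.

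Second, 0.4 is only the bottom of the stated range, and the preliminary values in C.6.2 and C.7 are higher (0.84, above 0.55, and above 0.45 in absolute size). This stands: the shortfall is confined to adjusted correlations between 0.40 and about 0.45. But the 0.84 comes from six people, the C.7 values are cross-sectional rather than correlations of changes, and neither section mentions covariates. D.8 itself keeps 0.4 within the range to which its power claim is attached.

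Third, covariates can raise power by removing outcome variance. That also stands, and step 5 allows for it. The D.7 remark that they should have little impact settles nothing here. Its reason is matching between arms, which does not say how much change the covariates explain within an arm.

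Finally, enrolment is closed (Section 11.1) and visits stopped on 09/30/2022 (Section 20), so a restatement cannot change the sample size. Its use is in the reading of null results.

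**Conclusion.** The concern holds in a limited form. For the covariate-adjusted per-arm regression, the claim of power above 0.85 is not met at the low end of D.8's own range:

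- about 0.74 to 0.75 if 0.4 is the adjusted correlation, or if the covariates explain little outcome variance;
- about 0.77 to 0.85 if 0.4 is unadjusted and the covariates independently explain 5 to 20% of outcome variance;
- about 0.85 to 0.86 at an adjusted correlation of 0.45, and 0.92 to 0.93 at 0.50.

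This assumes measured predictors and covariates, one term per covariate, 50 complete cases and analysis within each arm. If both arms were pooled (N = 100), power at 0.4 would be about 0.98 even with the covariates, but D.6 and D.8 point to a per-arm test.

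Two stronger readings should be avoided. A single power of 0.75 for Hypothesis 6 cannot be asserted, because the documents do not say whether 0.4 is adjusted. Nor is Hypothesis 6 underpowered across its stated range: from about 0.45 upward the single-variable claim is met or very nearly so.

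**What to change.** In D.8, add three statements to the Hypothesis 6 power:

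1. whether the range 0.4 to 0.8 refers to correlations adjusted for the D.7 covariates and BDI-II;
2. which G*Power procedure was used and how many predictors were entered;
3. the single-variable power of the covariate-adjusted regression in one arm of 50, treating predictors as measured: about 0.75 at an adjusted correlation of 0.4, and above 0.85 only from about 0.45 upward.

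The cost is a few sentences and a less favourable stated power. Sample size, visits and the planned analysis do not change.

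Reducing the primary covariate set is optional and not part of this correction. With two covariates, simulated power at 0.4 is about 0.82, still short of the claim, and the reduction would drop from the primary model variables for which the plan chose to adjust.

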Hypothesis 5: Compared with the sham group, mTBI Veterans in the IASIS treatment group will also show significantly greater decreases in PTSD symptoms between baseline and post-treatment assessments.

Specific Aim 3: To study the relationship among IASIS treatment-related changes in rs-MEG slow-wave imaging, PCS, and neuropsychological measures in Veterans with mTBI. We will correlate changes between baseline and post-IASIS abnormal rs-MEG slow-wave generation (i.e., total abnormal rs-MEG slow-wave and voxel-wise source imaging measures) with changes in PCS and neuropsychological tests performance.

Hypothesis 6: Reduced MEG slow-wave generation will correlate with reduced total PCS score, individual PCS scores (e.g., sleep disturbance, post-traumatic headache, photophobia, and memory problem symptoms), and improved neuropsychological exam scores between post-IASIS and baseline exams.

Section 7 - Background and Significance

7) Provide a succinct discussion of relevant background information to justify performing the proposed study.

B. Background

B.1 Challenges of Neuroimaging Techniques in Detecting Mild TBI

Mild TBI (mTBI) is a leading cause of sustained physical, cognitive, emotional, and behavioral deficits in OEF/OIF/OND Veterans with combat-related exposure to blast as a primary cause. In the general population, the majority (75%) of TBIs are in the "mild" range of severity (mTBI) [24]. A combat-related TBI study showed that 89% of all TBIs were mild [23]. However, the pathophysiology of mTBI is not completely understood, the long-term effects of mTBI are controversial, and there have been few effective treatments for mTBI. Although post-concussive symptoms (PCS) in mTBI resolve by three months after injury in the majority of individuals [40], about 20% (varying from 8-33%) of mTBI patients show persistent PCS and long-term cognitive and/or behavioral impairments [40,41]. It is unclear why similar mTBI events can lead to dramatic neurobehavioral decompensation with persistent PCS in some patients, but not in others [42]. In the majority of acute and particularly chronic mTBI patients, CT and MRI are generally negative [43-45], even in individuals with persistent PCS and cognitive and/or behavioral deficits. This finding highlights the limited diagnostic and treatment-assessment values of

conventional CT and MRI, especially in the chronic phase.

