
C.7 MEG Correlated with PCS Scores and Neuropsychological Scores in mTBI

MEG slow-wave correlates with PCS score in mTBI: Voxel-wise correlational analyses of MEG slow-wave measures and PCS were performed in the blast and non-blast mTBI groups described in C.2. Significant positive correlations were found between MEG source magnitude and PCS scores (Fig. 8, $r>0.55$) [1]. In the blast mTBI group, personality symptoms (e.g., social problems) correlated with MEG slow-waves in bilateral OFC and medial PFC; trouble concentrating and affective lability both correlated with slow-waves in left OFC; blurred vision/visual difficulties correlated with slow-waves in right fusiform gyrus. In the nonblast mTBI group, depression symptoms correlated with slowwaves in ACC. In combined blast and non-blast mTBI groups, only MEG source magnitude from right OFC correlated with trouble concentrating (not shown). The threshold of the voxel-wise analyses was at $q=0.05$ by FDR [85]. These results support Hypothesis 6. MEG slow-wave correlates with neuropsychological scores in 31 mTBI patients: Fig. 9 shows brain regions with negative correlations ($|r| > .45$) between rs-MEG slowwave magnitude and performance on DKEFS Color Word Interference test. Specifically, poorer inhibitory control was associated with higher rs-MEG slow-wave magnitude in the right dIPFC, bilateral supramarginal gyri, ACC, right hippocampus, and left inferior temporal lobe. These results also support Hypothesis 6. **Figure 8 and 9**

- See attached document.

C.8. Preliminary Data for Nexalin

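### The power above 0.85 for Hypothesis 6 holds for one total-score correlation at |r| = 0.4, not for the voxel-wise correlations that Aim 3 and D.6 also plan

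*Combined protocol and SAP*

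**What the plan says.** Specific Aim 3 (Section 6) spells out the MEG quantity to be correlated with symptoms and test scores as "total abnormal rs-MEG slow-wave and voxel-wise source imaging measures". Section D.6 repeats this: it will correlate "changes in the total abnormal MEG Z-scores as well as voxel-wise Z-score MEG source imaging measures with changes in PCS", with false discovery rate (FDR) control at q < .05, and it plans the same pair of MEG measures for the neuropsychological tests. D.6 says the voxel-wise analysis may add spatial information for each symptom category. It does not say which of the two MEG measures decides Hypothesis 6.

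Section D.8 expects |r| of about 0.4 to 0.8, citing C.6 and C.7, and states that with 50 per mTBI group and two-tailed alpha 0.05 "the estimated powers are > 0.85 for changes in MEG slow-wave correlating with total PCS score or one NP variable". The next sentence claims equal power for five PCS or neuropsychological variables under Bonferroni, and for more than five under FDR. On method it says only "We used G*Power (University of Dusseldorf) for the power analysis", without naming the test. All the multiplicity considered for Hypothesis 6 is across outcome variables, and none is across voxels.

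The effect sizes from C.7 are themselves voxel-wise. For the PCS correlations there, "The threshold of the voxel-wise analyses was at $q=0.05$ by FDR". D.2 puts the source grid at about 10,000 nodes.

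**The concern.** D.8 gives one power figure for the MEG change without saying which MEG measure it covers, and it draws its effect size partly from voxel-wise results. A reader can therefore take 0.85 to apply to the maps. A voxel-wise test at q < .05 uses a far stricter cut-off per voxel than 0.05, so power for each voxel must be lower.

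The C.7 correlations (r > 0.55 for PCS, |r| > .45 for the inhibition test in 31 patients) are also a weak basis for relying on the upper end of the range. The PCS values belong to voxels that passed a threshold and the others to the regions displayed. Values selected in this way tend to overstate the true correlation.

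What is at stake is interpretation. If the maps are thought to have 0.85 power, a sparse map may be read as evidence against a regional relation, or the few surviving voxels may be taken as its full extent.

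**Working it through.** **Inputs.** From D.8: N = 50 per group, two-tailed alpha 0.05, lower end of the effect range r = 0.4. From D.6: q = 0.05. From D.2: about 10,000 nodes (the count left after the normative mask in D.3.2 is not given). Assumed, because the documents are silent: the share π of voxels that truly correlate with the outcome.

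**Reproducing the printed figure (one test, r = 0.4).**

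- Noncentral t: ncp = r√N / √(1 − r²) = 0.4 × 7.071 / 0.9165 = 3.086. With 48 df the critical value is 2.011, and power = 0.856.
- Fisher z: atanh(0.4) × √47 = 2.904, and 2.904 − 1.960 = 0.944, so power = 0.83. Simulation of the exact test also gives 0.83.

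So the printed value is that of one unadjusted test at the bottom of the planned range. A comparison at r = 0.4 is like for like.

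**Voxel-wise power.** With many tests, the Benjamini-Hochberg cut-off t solves

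t = q × [(1 − π) × t + π × Power(t)].

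Check at π = 10%: 0.05 × (0.9 × 0.00242 + 0.1 × 0.462) = 0.0024, which returns t. Results at r = 0.4, N = 50:

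| Assumed share π | Cut-off t | Power per true voxel, noncentral t | Same, Fisher z |
|---|---|---|---|
| 1% | 0.000065 | 0.12 | 0.15 |
| 5% | 0.00089 | 0.34 | 0.34 |
| 10% | 0.0024 | 0.46 | 0.44 |
| 20% | 0.0061 | 0.59 | 0.56 |
| 50% | 0.019 | 0.74 | 0.71 |
| 90% | 0.037 | 0.82 | 0.79 |

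Simulation with 10,000 independent tests gave 0.15, 0.34, 0.45, 0.56 and 0.71 for 1%, 5%, 10%, 20% and 50%. Correlating the voxels in blocks changed these averages little.

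**Correlation needed for 0.85 per voxel** (noncentral t): 0.57, 0.52, 0.50 and 0.47 for shares of 1%, 5%, 10% and 20%. At r = 0.5, power is 0.58, 0.79, 0.86 and 0.91 for the same shares. At r = 0.55 it is 0.80, 0.92, 0.95 and 0.97.

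**Chance that at least one true voxel passes** (simulation, r = 0.4, 10,000 voxels). With blocks of 50 voxels correlated at 0.7, it was about 0.55 at 1%, 0.97 at 5%, and 1.00 at 10% and 20%. With independent voxels it was 0.97 at 1% and 1.00 from 5% up. With blocks of 100 correlated at 0.9, it was 0.19 at 1%, 0.79 at 5%, 0.96 at 10% and 0.99 at 20%.

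**The next sentence in D.8.** Bonferroni over five variables gives alpha = 0.05 / 5 = 0.01. At r = 0.4 the noncentral t form gives 0.66 (critical value 2.682), and Fisher z gives 2.904 − 2.576 = 0.328, so 0.63. Power of 0.85 at that alpha needs r of about 0.47 to 0.48. No outside assumption is involved.

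**The case against.** The strongest reply is that the figure above 0.85 is not wrong. D.8 ties it to one outcome at alpha 0.05, and 0.856 confirms it. C.6.2 reports a single correlation of total abnormal Z-score change with total RPQ change (r = 0.84), which fits a total-score reading. For Hypothesis 3, D.8 names voxel-wise and total scores explicitly, while for Hypothesis 6 it does not. This stands, so the defect is a figure whose scope is left open and a missing figure for the maps. A reader might infer that the single-test power was miscalculated, and the documents do not support that.

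Second, average power per true voxel is a different quantity from the power of one prespecified test, and Hypothesis 6 can be tested without recovering every voxel. This also stands. A reader might infer that an empty map is the likely result, but the simulations contradict that except near a 1% share with correlated voxels. Nor does D.6 promise a complete regional map, since it says only that the maps may be informative.

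Third, r = 0.4 is the floor of the range, and the true-voxel share is not in the documents. A reader might take 0.1 to 0.6 as the voxel-wise power without conditions. It is not: the range depends on the assumed share, and power rises quickly with r. The direction is firmer than the range, because at r = 0.4 power stays below 0.85 at every share tried, including 90%.

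D.8 also admits that one sample size cannot serve all hypotheses equally. That does not tell the reader which part of Hypothesis 6 is less well served.

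**Conclusion.** The concern holds in limited form. Power above 0.85 is right for one unadjusted total-score correlation at |r| = 0.4 under the noncentral t form, and slightly optimistic under Fisher z. It does not carry over to the voxel-wise half of Hypothesis 6 at that correlation. There, power per true voxel runs from about 0.12 to 0.74 for assumed shares of 1% to 50%, and an incomplete map is the expected result.

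The claim of equal power for five Bonferroni-corrected variables does not reproduce at |r| = 0.4, where it is about 0.63 to 0.66.

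The figures assume 50 analysable participants, no covariates and one common true correlation across the affected voxels. Dropout, or the degrees of freedom spent on the D.7 covariates, would lower them at the same correlation.

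**What to change.** In D.8:

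- Restrict the statement of power above 0.85 to the total abnormal MEG Z-score with one outcome at |r| = 0.4, and name the G*Power test used.
- Add that voxel-wise power at q < .05 is lower at |r| = 0.4, giving the range with the assumed share of true voxels beside it, and that 0.85 per voxel needs |r| of about 0.47 to 0.57 for shares of 20% down to 1%.
- Replace the claim for five variables with about 0.63 to 0.66 at |r| = 0.4, or state the correlation of about 0.47 to 0.48 at which 0.85 is reached.

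In D.6, state that the total-score regression decides Hypothesis 6 and that the voxel-wise maps serve localisation, so that a sparse map is not read as a negative result.

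The cost is rewording in two sections and a less favourable power statement. No new data are needed. Section 20 records that study visits stopped on 09/30/2022, so the sample size cannot be changed and only the interpretation can still be settled.

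### Hypothesis 6: power above 0.85 for five correlations under Bonferroni needs |r| of about 0.47–0.48; at the plan's lower end of 0.4 it is about 0.63–0.66

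*Combined protocol and SAP*

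**What the plan says.** The power analysis in Section 9, D.8 expects correlations for Hypothesis 6 of roughly 0.4 to 0.8 in absolute value, citing the pilot results in C.6 and C.7. "With N=50 in each mTBI group, two-tailed" and at alpha 0.05, it puts power above 0.85 "for changes in MEG slow-wave correlating with total PCS score or one NP variable". The next sentence extends this: "The same level of power can be achieved for 5 symptom individual PCS / NP variables at" alpha 0.05 "in the conservative case of Bonferroni correction, and for more than 5" variables when FDR is used. No new correlation and no new sample size are given for the five-variable statement.

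The analysis is set out in D.6: "Linear regression analyses will be performed for the correlation analysis, and FDR will be used to control family-wise error". Hypothesis 6 in Section 6 covers the total PCS score, "individual PCS scores (e.g., sleep disturbance, post-traumatic headache, photophobia, and memory problem symptoms") and neuropsychological scores. For the cognitive measures D.6 adds: "We also predict that in mTBI-IASIS group, but not in the sham group, reduction in MEG slow-wave generation will correlate with" improvement across domains.

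**The concern.** Dividing alpha by five while holding the sample size and the correlation fixed must lower the power of each test. If the single-test figure of just over 0.85 belongs to the lower end of the expected range, the five-variable figure at that same point cannot also exceed 0.85.

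The individual symptom and cognitive links are where a reader would use this sentence. As written, it says each of five links would be missed less than 15% of the time even under the strictest correction the plan mentions. A null result for, say, headache or memory would then look better excluded than 50 participants allow.

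**Working it through.** **Inputs**
- Expected |r|: about 0.4 to 0.8 (D.8).
- Sample size per correlation: 50. D.8 ties power to each mTBI group separately.
- Alpha: 0.05 two-sided for one test (D.8). With five tests under Bonferroni, 0.05 / 5 = 0.01 each.
- Method: linear regression (D.6), software G*Power (D.8). The G*Power routine is not named, so two standard models are used.

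**Formulas**
- *Regression (fixed predictor).* Noncentrality λ = N r² / (1 − r²). Power = P[F(1, N − 2; λ) > critical F].
- *Bivariate normal.* Exact power of the same test when both variables are random.

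**Step 1: reproduce the plan's single-test figure.** N = 50, r = 0.4:

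λ = 50 × 0.16 / 0.84 = 9.52. The critical F(1, 48) at 0.05 is 4.04. Power = **0.856**.

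This matches the stated lower bound at the bottom of the range. The bivariate normal model gives 0.835. At r = 0.45 the regression figure would already be 0.937, so the stated figure fits |r| = 0.4.

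**Step 2: the same inputs at 0.01 per test.** λ is unchanged at 9.52. The critical F(1, 48) rises to 7.19. Power = **0.657** (regression) or **0.634** (bivariate normal).

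**Step 3: across the range** (N = 50, two-sided 0.01)

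| Absolute r | Regression | Bivariate normal |
|---|---|---|
| 0.40 | 0.657 | 0.634 |
| 0.45 | 0.806 | 0.779 |
| 0.47 | 0.855 | 0.827 |
| 0.48 | 0.877 | 0.849 |
| 0.50 | 0.914 | 0.888 |
| 0.60 | 0.994 | 0.986 |

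Power equals 0.85 at |r| = 0.468 (regression) or 0.480 (bivariate normal).

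**Step 4: sample size for 0.85 at |r| = 0.4 and alpha 0.01.** Regression needs 72 per group. Bivariate normal needs 76 (75 gives 0.8496). The plan has 50.

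**Step 5: variants at N = 50 and |r| = 0.4.** One-sided 0.01 gives 0.72–0.75, the Šidák correction about 0.63, and allowing for 9 to 12 covariate degrees of freedom about 0.64–0.65. None reaches 0.85.

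**Step 6: comparison with FDR.** Benjamini–Hochberg at q = 0.05 with five variables, N = 50 and |r| = 0.4 was simulated. The documents give neither the correlation among the variables nor the number of real links, so both are assumed. With intercorrelation 0.2 to 0.6, power per link is 0.80–0.81 if all five links are real and 0.74–0.75 if three are. A second simulation, with all five or all ten links real and test correlation 0 to 0.5, gives 0.78–0.81.

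**The case against.** The best case for the plan has four parts.

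- **Most of the range is fine.** D.8 gives an approximate range and attaches no particular correlation to the five-variable sentence. Power exceeds 0.85 from about 0.47–0.48 up to 0.8, roughly four-fifths of that range. This is true and limits the finding. But the single-test bound fits the lower end, and claiming the same level of power carries that bound over to a point where it fails.
- **The pilot correlations were larger.** C.6.2 reports 0.84 for total RPQ change. C.7 reports values above 0.55 for PCS and above 0.45 in magnitude for the DKEFS test. At 0.55, Bonferroni power is 0.972 (regression) or 0.954 (bivariate normal). However, the first value comes from six people and the C.7 symptom correlations were selected by a voxel-wise threshold. With these data in hand the plan still set its lower end at 0.4. At 0.45, power is 0.78–0.81.
- **Pooling might be intended.** D.6 mentions both groups when introducing the symptom correlations, and 100 participants would give about 0.95 at |r| = 0.4 and alpha 0.01. D.8, however, states its power for 50 per group, and D.6 predicts the cognitive links in the IASIS group only.
- **Bonferroni is not the planned correction.** This stands: the 34–37% miss rate describes the conservative case, not the FDR analysis. It lowers the practical weight but does not make the stated figure right, and the FDR simulations at |r| = 0.4 also stay below 0.85.

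Enrolment has closed (Section 11.1) and visits stopped on 09/30/2022 (Section 20), so the point affects how results are read, not how the trial is run.

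**Conclusion.** The five-variable Bonferroni statement is wrong as written at the lower end of the plan's own range. Power per correlation at |r| = 0.4 is about 0.63–0.66, so the miss rate is about 34–37% instead of under 15%. The claim becomes true from |r| of about 0.47 (regression) or 0.48 (bivariate normal).

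This rests on 50 analysed participants per correlation, two-sided tests at 0.01 each, and power counted per test. The chance that all five are significant would be lower. The power section states no dropout allowance, and any loss would reduce power further. The single-variable figure is sound at |r| = 0.4 under the planned regression and about two points lower (0.835) under a bivariate normal model.

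This is a reproducible overstatement that should be corrected. It is confined to the Aim 3 correlations and to a correction that is not the planned one.

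**What to change.** In D.8, replace the five-variable Bonferroni statement with:

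> For five variables with Bonferroni (alpha 0.01 each, N=50), power per correlation is about 0.63–0.66 at |r|=0.4 and reaches 0.85 only for |r| of about 0.47–0.48 or more.

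Leave the single-variable figure, the planned FDR analysis and the list of Hypothesis 6 correlations as they are. The adjoining clause on more than five variables under FDR could usefully be qualified in the same edit, stating the correlation, the number of real links and the intercorrelation assumed.

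The cost is one sentence and a less favourable stated figure. Nothing changes in sample size, analysis or what happens to participants.
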